9.2 SAFETY

9.2.1 Baseline demographic characteristics

Baseline demographic characteristics at screening will consist of:

1. Age (years)
2. Height (cm): should be measured when the subject's shoes are off, feet together, and arms by the sides. Heels, buttocks, and upper back should also be in contact with the wall when the measurement is made.
3. Body weight (kg): should be obtained with the subject wearing undergarments or very light clothing and no shoes, and with an empty bladder. The floor surface on which the scale rests must be hard and should not be carpeted or covered with other soft material. The same scale should be used throughout the study, and calibrated on a regular basis as recommended by the manufacturer.
4. Body mass index
5. Race and/or ethnicity
6. Gender

9.2.2 Medical history

Medical history along with subject demographics will be obtained at screening, including history of diabetes (e.g., age at onset of diabetes, start and stop dates of previous insulin treatments, treatment name, dose(s), frequency and method of dose delivery, date of clinical diagnosis of T1DM).

Determination of the relevance of the medical history, and its impact on subject eligibility, will be made by the Investigator or designee. The Investigator may consult with the Sponsor medical monitor if necessary.

9.2.3 Screening assessment

Informed Consent/Accent will be obtained prior to performing any screening procedures. The safety assessment at screening will be performed according to the Flow Chart 1.1 and will include:

- Assessment of inclusion and exclusion criteria
- Physical examination (at screening): full physical examination, including ear, nose, throat, lung and cardiac auscultation, recording of Tanner stages of pubertal development and excluding genitourinary and rectal examinations
- Oral body temperature, body weight, and height
- Vital signs (respiratory rate, sitting blood pressure, and pulse measurements) will be recorded with the subject in a sitting position for 5 minutes before the measurement is taken.
- HbA1c

- Fasting serum C-peptide
- Laboratory tests:
 - Serology tests: hepatitis B antigen, hepatitis C antibodies, anti-HIV-1 and anti-HIV-2 antibodies
 - Anti-Insulin Antibody
 - Pregnancy test: females of childbearing potential
 - Urine cotinine
 - Urine drug screening: amphetamines/methamphetamines, barbiturates, benzodiazepines, cannabinoids, cocaine, and opiates
 - Alcohol breath or plasma test
 - Hematology: red blood cell count, hematocrit, hemoglobin, white blood cell count with differential count (neutrophils, eosinophils, basophils, monocytes, and lymphocytes), platelets
 - Biochemistry:
 1. Plasma/serum electrolytes: sodium, potassium, chloride, calcium, phosphorus, carbon dioxide
 2. Liver function: aspartate aminotransferase, alanine transaminase, alkaline phosphatase, total and conjugated bilirubin
 3. Renal function: blood urea nitrogen, creatinine, uric acid
 4. Metabolism: albumin, total proteins, total cholesterol, low-density lipoprotein, triglycerides
 5. Potential muscle toxicity: creatinine phosphokinase, lactate dehydrogenase
 - Urinalysis: albumin/creatinine ratio, ketones, glucose, erythrocytes, and leucocytes count, pH, urobilinogen, nitrates, specific gravity
- A standard 12-lead electrocardiogram recorded after at least 10 minutes in a supine position
- FEV₁ testing: Spirometry (FEV₁) will be done to assess pulmonary function. Another pulmonary function test may be done after consultation with a pediatric pulmonologist if the subject is unable to perform spirometry
- Adverse events (AEs) spontaneously reported by the subject or observed by the Investigator will be monitored
- Prior/concomitant medications reported by the subject or by the Investigator will be

recorded

9.2.4 Safety assessment during the study

Safety assessments during the study will be done according to the Flow Chart 1.1 and will include, but is not limited to:

- Physical examination: the abbreviated physical examinations will include, but not limited to, general appearance, mental status, respiratory and cardiovascular systems, and other evaluations deemed appropriate by the Investigator for safety reasons
- Body weight (kg)
- Vital signs (respiratory rate, sitting blood pressure, and pulse measurements) will be recorded after the subject has been sitting for 5 minutes
- Laboratory tests:
 - Urine pregnancy test: females of childbearing potential
 - Urine cotinine
- Adverse events spontaneously reported by the subject or observed by the Investigator will be monitored
- FEV₁ testing: Spirometry will be done to assess pulmonary function. Another pulmonary function test may be done after the consultation of a pediatric pulmonologist if the subject is unable to perform spirometry
- Concomitant medications reported by the subject or by the Investigator will be recorded

9.2.5 Self-measured blood glucose (SMBG)

Blood glucose values will be self-measured by the subject using the Sponsor-provided blood glucose meter and corresponding supplies (lancets, control solutions, test strips, etc). Subjects will enter their SMBG data in the Sponsor-provided e-Diary.

Post-dose SMBG will be used to adjust the bolus insulin. The frequency of monitoring, including ad hoc values, can be adjusted by the Investigator.

All SMBG values will be used by the Investigator to monitor glycemia.

9.2.6 Mandatory SMBG

9.2.6.1 Fasting pre-breakfast SMBG

Fasting pre-breakfast SMBG will be measured daily during the study and used, among other things, to titrate basal insulin doses.

9.2.6.2 Routine SMBG monitoring

In addition to performing fasting SMBG every morning before breakfast, subjects or parents will perform SMBG monitoring 120-150 minutes post-dose at each meal. AFREZZA® doses will be adjusted based on these measurements ([Table2](#)).

9.2.6.3 7-point SMBG profiles

Once during the screening period in the week prior to the PK visit (Visit 2) and once per week during the treatment period 7-point glucose data (pre-meal and 120-150 minutes post-dose at breakfast, lunch, and dinner as well as at bedtime) will be obtained via SMBG readings. These data will be reviewed by the site and may be used to prescribe a regular supplemental post-meal AFREZZA® dose as per Section [8.1.5](#).

On these days, the starting and ending time for each meal will be reported in the e-Diary and in the e-CRF.

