8.1.5 Postprandial dosing (follow-on doses)

If a subject's SMBG is greater than or equal to 180 mg/dL, 120 to 150 minutes after the prandial dose, the subject should take an additional, individualized postprandial or follow-on dose. The dose should be sufficient to reduce blood glucose below 120 mg/dL based on the subject's individualized dose-response.

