- Pre-breakfast SMBG values will be obtained (for basal insulin adjustments) and recorded for this visit as well as for the duration of the study.
- Study site staff will explain to subjects/parents how to titrate the prandial dose for each meal based on the 120 to 150 minute post-dose SMBG values.
- Study site staff will explain to subjects/parents how to determine the appropriate postprandial or follow-on dose based on the value of 120 to 150 minute post-dose SMBG.
- Instructions will be provided on proper use and storage of AFREZZA® (inhaler and cartridges), and subjects/parents will be reminded to bring all cartridges back to the site with them at their next visit.
- Nutritional information will be provided (e.g., including carbohydrate content of meals and its impact on insulin requirements). Subjects will receive information about the importance of maintaining stable carbohydrate content of meals throughout this study.
- Glucose meter test strips and Afrezza cartridges will also be provided.

Discharge

Subjects will be discharged from the clinic after the completion of PK sampling (4 hours), lunch, an abbreviated physical examination and vital signs.

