5.5 Study Drug Exposure

For each subject, information regarding study drug exposure will be derived from the eCRF and study drug dosing eDiary data. Here is a summary:

- First dose date is defined as the date the first study drug dose is taken, as shown in the eCRF ('AFREZZA[®] dosing' page at Visit 2).
- Last dose date is defined as the date the last study drug dose is taken, as shown in the eDiary.
- Period-specific treatment start date:
 - Treatment start date in the titration period is defined as Study Day 1.
 - Treatment start date in the extension period is defined for subjects who participate in the extension period only, as the date the first study drug dose is taken after the date of Visit 15.
- Period-specific treatment end date:
 - Treatment end date in the titration period is defined as:
 - The date the last study drug dose is taken, for subjects who do not participate in the extension period;
 - The date the last study drug dose is taken prior or on the date of Visit 15, for subjects who participate in the extension period
 - Treatment end date in the extension period is defined for subjects who participate in extension period only, as the date the last study drug dose is taken.
- Total Exposure time (days) is defined as last study dose date – first study dose date +1.
- Period-specific exposure time (days) is defined as period-specific treatment end date – period-specific treatment start date +1.
- Total daily dose is defined as the sum of all doses of AFREZZA[®] taken during a day.
- Prandial dose at a meal is defined as the sum of the pre-meal dose and the post-meal dose given at that meal. Per protocol, subjects should take a dose at beginning of each meal, and the post-meal dose will be given as needed to keep the blood glucose level in control.

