8.4.2 Extent of Study Drug Exposure

Detailed dosing information of AFREZZA[®] will be collected from the first dose to the last dose through the trial. Information of doses given during the PK Visit is captured on the eCRF, while other dosing information is captured on the eDiary.

Table Presentation

Dosing information at the PK Visit will be summarized by cohort, and presented in a subject-level listing.

For total exposure time, both numerical and categorical summaries will be provided by cohort and study period. For AFREZZA[®] doses collected on the eDiary, the following will be derived and summarized by cohort. For Cohort 1 and Cohort 2, additional summaries will be provided by starting dose, as appropriate.

- Average total daily dose of AFREZZA[®] at weekly intervals for the titration period, and at monthly intervals for the extension period. For each time interval, only data collected in the 2nd half of the interval (i.e., within 3 days prior to the each clinic visit in the titration period and within 2 weeks prior to each visit in the extension period) will be included in the summary. If a visit is performed, the actual visit date will be used to determine the time frame; if a visit is not performed, the target visit date will be used to determine the time frame. Average total daily dose is defined as the average of all total daily doses taken within a time frame. For each time interval, average total daily dose will be calculated for each subject first, and then summarized by cohort.
- Average prandial dose of AFREZZA[®] by meal at weekly intervals for the titration period, and at monthly intervals for the extension period, calculated using the same method as described above

Moreover, the use of post-meal (i.e., supplemental) doses will be presented in a summary table, by cohort and study period. Both subject-level summary (number and percentage of subjects

taking at least one post-meal dose) and dose-level summary (e.g., number of post-meal doses indicated, number of doses given, etc.) will be provided.

Graphic Presentation

Average total daily dose of AFREZZA[®] and average prandial dose of AFREZZA[®] by meal will be plotted over time to illustrate dose change throughout the study.

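### Protocol 9.2.6.3 allows a 'regular' post-meal dose that 8.1.5 does not describe, so it is unsettled what happens when the current reading is below the trigger and what SAP 8.4.2 should count as 'indicated'

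*Protocol*

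**What the plan says.** Protocol 9.2.6.3 has children collect a 7-point profile in the week before Visit 2 and then weekly on treatment. The site reviews these profiles, and they "may be used to prescribe a regular supplemental post-meal" AFREZZA dose, with 8.1.5 cited as the authority.

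Protocol 8.1.5 describes a different kind of dose. The child should take an individualized follow-on dose if the SMBG "is greater than or equal to 180 mg/dL, 120 to 150 minutes after the prandial dose", sized to bring glucose below 120 mg/dL. Protocol 8.1.4 also conditions the dose on the current reading, but with a strict inequality (above 180 mg/dL). At Visit 2, under 12.1.2, staff teach families "how to determine the appropriate postprandial or follow-on dose based on the value of 120 to 150 minute post-dose SMBG".

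SAP 5.5 says "the post-meal dose will be given as needed to keep the blood glucose level in control". SAP 8.4.2 plans a dose-level summary of post-meal doses, giving as examples "number of post-meal doses indicated, number of doses given". The SAP text does not define 'indicated'. The change log in SAP section 9 gives the reason for adding this table: to see how frequently supplemental doses need to be given. Appendix 3 lists it as Table 14.1.2.7 and marks it for the DMC package.

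**The concern.** A standing dose prescribed from a past profile and a dose triggered by the current reading are different rules. They agree when the current reading reaches the trigger. Below the trigger, the protocol does not say whether a child with a 'regular' post-meal prescription takes the dose.

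Two things are at stake. The first is safety: this is a second insulin dose about two hours after a meal in children aged 4 to 17, hypoglycemia is a listed safety endpoint, and Protocol Table 1 lists severe hypoglycemia as an important identified risk. The second is interpretation. The third objective concerns titrating prandial and supplemental doses from readings taken 120 to 150 minutes after each prandial dose, and Protocol 4.2 says the data will inform dosing in Part 2. A standing dose shows what was prescribed and not what was needed, so mixing the two blurs a table meant to show need.

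**Working it through.** The plan states no figure on this point. The main check sets the passages side by side.

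| Place | What prompts the post-meal dose | Regular dose mentioned? |
|---|---|---|
| Protocol 8.1.4 | Current reading above 180 mg/dL | No |
| Protocol 8.1.5 | Current reading at or above 180 mg/dL | No |
| Protocol 12.1.2 | Current 120 to 150 minute reading | No |
| Protocol 9.2.6.3 | Site review of weekly profile, citing 8.1.5 | Yes |
| SAP 5.5 | As needed; no reading or threshold named | No |

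Only 9.2.6.3 speaks of a regular dose. The section it cites does not say how such a dose is prompted, how it is sized from a profile, or whether it is taken when that meal's reading is below 180 mg/dL. Sections 8.1.4 and 8.1.5 also differ at exactly 180 mg/dL, so 'indicated' has no single definition even without the regular dose.

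**How long a standing dose could run.** The flow chart schedules review of 7-point data at Visits 6, 9, 12 and 15. Visit 6 is Day 8. Supplies are returned at Visit 15, Day 29.

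- Duration at one meal a day: 29 − 8 = 21 days, so about 21 doses, give or take the ±1-day visit windows.
- Doses that bypass the trigger: 21 × (share of those readings below the trigger). The share is not stated. At 0% the count is 0, and at 100% it is 21.

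**Scale against a cohort of 14 over the 28-day titration period.**

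- Main-meal occasions: 14 × 3 × 28 = 1,176.
- One child's ceiling: 21 / 1,176 = 1.8% of occasions.
- If 10% to 30% of meals reached the trigger (an assumption, since the documents give no rate), triggered doses would number 0.10 × 1,176 ≈ 118 to 0.30 × 1,176 ≈ 353. One child's ceiling of 21 would then equal 21 / 118 ≈ 18% down to 21 / 353 ≈ 6% of that number.

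These are ceilings. A child given a regular dose because of repeated post-meal highs would be expected to meet the trigger on many of those days.

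**The case against.** The best defense is that the sentence in 9.2.6.3 ends by placing the dose under 8.1.5. On that reading, the weekly profile only helps set the size of a dose that stays conditional. A reader might infer that the two sections give opposite instructions for a low reading. The documents do not support that: 8.1.5 says to dose if the reading reaches the threshold, not only if, it gives no instruction below it, and 9.2.6.3 is permissive. SAP 5.5 is also looser than the protocol sections. Investigator judgment is expected elsewhere too: 12.1.3.1 allows discretion over mealtime doses, and 12.1.3.2 allows 7-point data to be used to adjust dosing.

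All of that stands, and it limits the point to an inconsistency. It does not remove it. If the dose stays conditional, 'regular' adds little, because 8.1.5 already individualizes the size. A site acting on the plain word has textual support as well.

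A reader might also infer that one such child adds 28 trigger-bypassing doses, that one or two children would dominate the cohort count, or that Table 14.1.2.7 becomes meaningless. None of these is shown. Scheduled on-treatment review starts on Day 8, even 28 doses would be 28 / 1,176 = 2.4% of occasions, and the table shells are in separate files that may define 'indicated'. Post-meal doses entering the SAP's prandial dose is no defect either, since SAP 5.5 defines prandial dose as the sum of the two.

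Finally, the analysis problem is recoverable. Doses and times are recorded daily (Protocol 9.2.8), and post-dose readings are taken at each meal and recorded (9.2.6.2 and 9.2.7).

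**Conclusion.** The point holds as an unresolved inconsistency on a safety-relevant dosing rule. Section 9.2.6.3 permits a regular post-meal dose by reference to a section that contains none, and sites could differ when the current reading is below the trigger.

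Its size cannot be fixed from the documents because the number of children given a regular dose is not stated. Per child, at one meal a day, exposure to a standing dose is about 21 days in the titration period. The number that bypasses the trigger lies between 0 and about 21. This assumes the dose is prescribed at the first scheduled on-treatment review and continues until supplies are returned. The likely effect on the post-meal summary is some blurring of need with prescription, and it could be separated from data already collected. The correction is worth making because it is cheap and touches both hypoglycemia and a stated objective.

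**What to change.** In the protocol, reconcile 8.1.4, 8.1.5, 9.2.6.3 and 12.1.2, with SAP 5.5 in step, so that one stated rule says when a post-meal dose is taken. That rule should cover a reading below the trigger and a reading of exactly 180 mg/dL. Which rule applies is a clinical decision for the sponsor, and no view on it is given here.

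In SAP 8.4.2, define 'indicated' by that rule, carry the definition into the shell for Table 14.1.2.7, and add a separate count, by cohort, of post-meal doses given when not indicated. This count can be derived by matching e-Diary dose times to the recorded post-dose SMBG values.

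The cost is a wording correction in the protocol, one definition and one extra row in the SAP table, and a memo to sites. No new data collection is needed.

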9.2.6.4 Self-monitored blood glucose during symptomatic hypoglycemia

Whenever the subjects feel hypoglycemic symptoms, glucose should be measured by the subject (or others, if applicable) if possible. Subjects should be instructed to measure plasma glucose levels prior to carbohydrate intake/administration of glucose whenever symptomatic hypoglycemia is suspected, unless safety considerations necessitate immediate carbohydrate/glucose rescue prior to confirmation.

Subjects have to document hypoglycemic events appropriately in their diaries and contact the Investigator as soon as possible following severe events for review and for decision on any necessary measures to be taken.

All hypoglycemia episodes will be documented on the “hypoglycemia specific form” in the e-CRF. This includes all symptomatic hypoglycemia events and asymptomatic hypoglycemia.

Hypoglycemia events fulfilling the criteria of a serious adverse event (SAE) will be documented on the SAE form in the e-CRF.

9.2.7 Recording of SMBG into the e-CRF

All mandatory SMBG readings will be recorded in the e-CRF. Subjects will record SMBG readings in the e-Diary. Refer to the Site Operations Manual regarding SMBG data upload.

9.2.8 Recording of insulin doses into the e-CRF

To assess the change in daily AFREZZA and basal insulin dose, appropriate documentation of administration times and doses in corresponding pages of the e-CRF is requested.

Subjects will document the doses and times of administration of AFREZZA® and basal insulin in the e-Diary on a daily basis.

9.3 OTHER ASSESSMENT

Information on the ability to use the AFREZZA inhalation device will be collected in the e-Diary.

10 SUBJECT SAFETY

The Investigator is the primary person responsible for taking all clinically relevant decisions on safety issues.

If judged necessary, the opinion of a specialist should be sought in a timely manner (e.g., acute renal failure, convulsions, skin rashes, angioedema, cardiac arrest, electrocardiographic modifications, etc).

10.1 ADVERSE EVENT MONITORING

All events will be managed and reported in compliance with all applicable regulations and included in the final clinical study report (CSR).

10.2 DEFINITIONS OF ADVERSE EVENTS

10.2.1 Adverse event

An AE is any untoward medical occurrence in a subject administered a pharmaceutical product and which does not necessarily have to have a causal relationship with this treatment. An AE can be any unfavorable and unintended sign (e.g., an abnormal laboratory finding), symptom, or disease temporally associated with the use of a drug, and does not imply any judgment about causality.

- **Mild** = no modification of daily activities and does not require corrective/symptomatic treatment.
- **Moderate** = hinders normal daily activities and/or requires corrective/symptomatic treatment.
- **Severe** = prevents daily activities and requires corrective/symptomatic treatment.

10.2.2 Serious adverse event

A SAE is any untoward medical occurrence that at any dose:

- Results in death, or
- Is life-threatening, or
- Requires inpatient hospitalization or prolongation of existing hospitalization, or
- Results in persistent or significant disability/incapacity, or
- Is a congenital anomaly/birth defect, or
- Is a medically important event:

Medical and scientific judgment should be exercised in deciding whether expedited reporting is appropriate in other situations, such as important medical events that may not be immediately life-threatening or result in death or hospitalization but may jeopardize the patient or may require medical or surgical intervention to prevent one of the other outcomes listed in the definition above. Note: Examples of such events are intensive treatment in an emergency room or at home for allergic bronchospasm, blood dyscrasias, convulsions, that do not result in inpatient hospitalization, or the development of drug dependence or drug abuse.

10.2.3 Adverse event of special interest

An AESI is an adverse event (serious or nonserious) of scientific and medical concern, specific to the IMP or program, for which ongoing monitoring and rapid communication by the Investigator to the Sponsor may be appropriate. Such events may require further investigation in order to characterize and understand them.

For AESIs, the Sponsor must be informed immediately (i.e., within 24 hours), per SAE notification guidelines described in Section 10.3.2, even if not fulfilling a seriousness criterion as an SAE.

The following adverse events are considered AESIs:

- Acute bronchospasm
- Clinically relevant decline in pulmonary function
- Hypersensitivity reactions, including anaphylaxis, which can occur with insulin products, including AFREZZA
- Diabetic ketoacidosis

